9.2. Hematologic Toxicity

9.2.1 On day 1 of each new cycle, patients must meet the following criteria:

- $ANC \geq 1.0 \times 10^9 /L$
- Platelet count $\geq 50 \times 10^9 /L$

9.2.2 If these conditions are not met on Day 1 of a new cycle:

- The next cycle of treatment will not be initiated until the above conditions (section 9.3.1) are met. If ANC and platelet counts do not satisfy the requirements above after 2 weeks of withholding treatment, the subject will go off therapy. Transfusions and growth factors are permissible.
- For patients not meeting day 1 criteria (section 9.3.1) for two cycles (non-consecutive), the study drug dose(s) will be modified for the next cycle based on dose reduction tables of section 9.2.

9.2.3 If a patient develops thrombocytopenia or neutropenia during the cycle, then the following actions would take place (see Thrombocytopenia/Neutropenia table below).

Thrombocytopenia	Lenalidomide	Carfilzomib
Fall to $< 25 \times 10^9/L$	Hold both Lenalidomide and Carfilzomib, follow CBC at least weekly or more frequently if clinically indicated. Hold prophylactic anti-coagulation.	
Return to $\geq 25 \times 10^9/L$	Resume lenalidomide at next dose reduction	Resume carfilzomib at full dose.*
Subsequent fall to $< 25 \times 10^9/L$	Hold both Lenalidomide and Carfilzomib, follow CBC at least weekly or more frequently if clinically indicated. Hold prophylactic anti-coagulation.	
Return to $\geq 25 \times 10^9/L$	Resume lenalidomide at next dose level reduction	Resume carfilzomib at full dose.*

*Carfilzomib may be dose reduced at the clinical discretion of investigator.

Neutropenia (Absolute Neutrophil Count)	Lenalidomide	Carfilzomib
Falls to $< 0.5 \times 10^9/L$ or to $< 1.0 \times 10^9/L$ with fever	Hold Lenalidomide and Carfilzomib. Add filgrastim if Grade 3 with fever (single temperature of $38.3^\circ C$ or sustained temperature of $38^\circ C$ for > 1 hour) or Grade 4. Follow CBC at least weekly or more frequently if clinically indicated.	
Returns to $\geq 1.0 \times 10^9/L$	Resume Lenalidomide at next dose reduction.	Resume Carfilzomib at full dose.*
Subsequent drop to $< 0.5 \times 10^9/L$ or to $< 1.0 \times 10^9/L$ with fever	Hold Lenalidomide and Carfilzomib. Add filgrastim if Grade 3 with fever or Grade 4. Follow CBC at least weekly or more frequently if clinically indicated.	
Returns to $\geq 1.0 \times 10^9/L$	Resume Lenalidomide at next dose reduction.	Resume Carfilzomib at full dose.*

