11.4 Daratumumab

Among the 151 subjects treated with 16 mg/kg daratumumab as monotherapy in Studies GEN501 (NCT00574288) and MMY2002 (NCT01985126), the most frequently reported AEs (reported in >10% of subjects) were fatigue (29%); anemia (23%); nausea (19%); back pain (18%); cough (17%); thrombocytopenia (16%); decreased appetite (13%);

pyrexia, dyspnea, upper respiratory tract infection (12% each); nasal congestion and neutropenia (11% each). Grade 3 and higher AEs were reported in 48% of subjects treated with 16 mg/kg monotherapy daratumumab. The most frequently reported Grade 3 or higher AEs were anemia (13%) and thrombocytopenia (9%). All other Grade 3 and higher AEs were reported in <5% of subjects. No death has been reported in our ongoing daratumumab-KRd study using 36 mg/m² twice weekly dosing.

Among the 283 patients who received daratumumab in combination with lenalidomide and dexamethasone in the POLLUX trial¹², the most frequently reported AEs (reported in >10% of subjects) were neutropenia (59%), anemia (31%), thrombocytopenia (27%), febrile neutropenia (6%), lymphopenia (6%), diarrhea (43%), fatigue (35%), upper respiratory tract infection (32%), constipation (29%), cough (29%), muscle spasms (26%), nasopharyngitis (24%), nausea (24%), pyrexia (20%), insomnia (19%), dyspnea (18%), back pain (18%), vomiting (17%), asthenia (16%), peripheral edema (15%) and pneumonia (14%). The most frequently reported Grade 3 or higher AEs were neutropenia (52%), anemia (12%), thrombocytopenia (13%), febrile neutropenia (6%), lymphopenia (5%), diarrhea (5%), fatigue (6%) and pneumonia (8%). All other Grade 3 and higher AEs were reported in <5% of subjects.

Likely Side Effects: those occurring in more than 10% or more than 10 out of 100 persons who receive Daratumumab:

- Infusion related reaction (see separate section)
- Infection of the upper respiratory tract infection such as nose, sinuses throat or airway
- Infection of the lung
- Low neutrophils (a type of white blood cell)
- Low platelets
- Low red blood cells
- Low lymphocytes (a type of white blood cell)
- Numbness/tingling of the hands, feet or limbs
- Headache
- Cough
- Shortness of breath
- Diarrhea
- Nausea
- Vomiting
- Muscle spasms
- Fatigue
- Fever
- Swelling of hands, feet or limbs

Less Likely Side Effects: those occurring in 10% or 10 out of 100 persons who receive Daratumumab:

- The flu

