The study includes safety suspension rules; throughout the study we will monitor for grade 3 or higher heart failure. These safety suspension rules will be applied separately in the two cohorts. In the event that the rule is crossed (see Table below), the study will be suspended for that cohort and all safety data will be reviewed by the PI. We will report all SAEs per standard guidelines (Section 17.2). In addition, throughout the study we will monitor for grade 4 or higher adverse events related to study drugs; if the PI notices there is a safety signal, the study will be suspended and all safety data will be reviewed by the PI.

Failure Type	# of failures needed to suspend the study	Failure rate in the population	Probability boundary is crossed
Heart failure/Ischemic heart disease (grade 3 or higher) Or grade 4 or higher adverse events due to study drug.	3 in the first 17 patients 4 in the first 29 patients 5 patients at any point	0.05	0.1
		0.2	0.95

The above numbers apply for each of the cohorts. Each cohort will be assessed independently.

Secondary Objective. Objectives 1, 2, and 3 below will be evaluated separately for the two cohorts.

1. To evaluate the safety and tolerability of the combination therapy. Toxicities will be summarized by grade and cycle of therapy. Patients who receive any study drug will be included in this assessment.
2. To evaluate the rates of best overall response (partial response (PR) or better), very good partial response (VGPR) or better, and complete response (CR) or stringent CR (sCR) for the evaluable patients. See section 12.0 for response definitions. Response proportions along with exact 95% confidence intervals will be reported.
3. Kaplan-Meier methods will be used to estimate overall and progression-free survival. . Patients who receive any study drug will be included in this assessment.
4. To compare MRD techniques of multi-parametric flow cytometry with 1) next-generation sequencing and 2) mass spectrometry using summary statistics. Rates of concordance for the measures will be estimated. This will be evaluated among all MRD assessments.

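### The text and table of the safety-suspension rule count different events, and the stated 10% crossing probability has no support if related grade 4 or higher adverse events are counted

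*Combined protocol and SAP*

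**What the plan says.** All of this stands in Section 14.0 (Biostatistics) of the combined protocol and SAP, and applies to each cohort separately.

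- **Text, numeric rule.** The paragraph before the table names one event: "throughout the study we will monitor for grade 3 or higher heart failure". A cohort is suspended when the tabulated rule is crossed.
- **Text, related grade 4 or higher events.** These come in afterwards as an additional activity with no count attached: "if the PI notices there is a safety signal, the study will be suspended and all safety data will be reviewed by the PI".
- **Table.** A single failure-type cell lists grade 3 or higher heart failure or ischemic heart disease, followed by "Or grade 4 or higher adverse events due to study drug". The boundary is "3 in the first 17 patients 4 in the first 29 patients 5 patients at any point". Under "Failure rate in the population" the table gives 0.05 and 0.2; under "Probability boundary is crossed" it gives 0.1 and 0.95.

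Ischemic heart disease is in the table but not in the text. The table makes no exception for haematologic events.

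**The concern.** Someone counting failures cannot tell whether a related grade 4 neutropenia is one of the three that would suspend a cohort within its first 17 patients. Under the text it is not; under the table it is.

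The choice also decides whether the table's tolerated rate is plausible. A 5% rate might suit severe cardiac events alone. It needs its own justification for a composite that includes every related grade 4 or higher event, and none is given. The protocol anticipates such events: Section 9.2 sets out holding and resuming treatment for neutrophils below 0.5 × 10⁹/L and platelets below 25 × 10⁹/L, and for repeat neutropenia says "Add filgrastim if Grade 3 with fever or Grade 4". The table may therefore count as failures events after which the protocol expects treatment to resume.

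**Working it through.** **Inputs.** Boundary: at least 3 failures by patient 17, 4 by patient 29, 5 by patient 41. Rates: 0.05 and 0.20. Maximum cohort size: 41. All are from Section 14.0.

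**Method.** Let p be the per-patient failure probability, with patients independent. Start from Binomial(17, p) and remove outcomes of 3 or more. Add Binomial(12, p) for patients 18–29 and remove totals of 4 or more. Add Binomial(12, p) for patients 30–41 and remove totals of 5 or more. The crossing probability is the sum of what was removed. Checking after every patient gives the same result as checking at 17, 29 and 41, because the threshold is constant within each segment.

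**Reproducing the plan at p = 0.05.**
- By patient 17: P(0, 1, 2 failures) = 0.4181, 0.3741, 0.1575, so the crossing probability is 1 − 0.9497 = 0.0503.
- Patients 18–29: a further 0.0269.
- Patients 30–41: a further 0.0174.
- Total: 0.0503 + 0.0269 + 0.0174 = 0.0946, or 0.0945 before rounding the parts (stated: 0.1).

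At p = 0.20 the parts are 0.6904 + 0.1857 + 0.0719 = 0.948 (stated: 0.95). Both printed figures reproduce.

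**Where the 10% stops holding.** Solving for a crossing probability of exactly 0.10 gives p = 0.051.

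**Other true rates for the counted event (assumed).**

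| True rate | By patient 17 | By patient 41 |
|---|---|---|
| 5% | 0.05 | 0.09 |
| 8% | 0.15 | 0.30 |
| 10% | 0.24 | 0.47 |
| 15% | 0.48 | 0.80 |
| 20% | 0.69 | 0.95 |

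**What the documents say about rates.** Section 3.0 cites grade 3/4 neutropenia of 17% and thrombocytopenia of 17% with carfilzomib, lenalidomide and dexamethasone (KRd) in newly diagnosed patients. Section 11.4 cites grade 3 or higher neutropenia of 52% with daratumumab, lenalidomide and dexamethasone. Neither gives grade 4 separately. As an illustration, assume that grade 4 makes up 10% to 50% of the cited neutropenia and that all of it is judged drug-related. Call that rate q. With an independent 5% cardiac rate, the composite is 1 − 0.95 × (1 − q).

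| Base | q | Crossing, no cardiac events | Composite with 5% cardiac | Crossing |
|---|---|---|---|---|
| 17% | 1.7% to 8.5% | 0.004 to 0.34 | 6.6% to 13.1% | 0.20 to 0.70 |
| 52% | 5.2% to 26% | 0.105 to 0.99 | 9.9% to 29.7% | 0.46 to 0.998 |

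This covers neutropenia only; other related grade 4 or higher events would add to q.

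**If "or" means two parallel boundaries.** With each event class at 5% and independent, the chance of crossing at least one is 1 − (1 − 0.0945)² = 1 − 0.820 = 0.18.

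**The case against.** The best defence is that the table makes a conditional statement: if the failure rate is 5%, the boundary is crossed with probability 0.1. That is right for any per-patient binary event, pooled or not. This stands, and there is no arithmetic error to report. A reader might infer that the 10% is impossible, or that expected cytopenias make suspension almost certain. The documents do not support either claim. They give no grade 4 rate, and on the 17% base without cardiac events the illustration never exceeds 0.34.

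A reader might also infer that pooling buries a true cardiac signal. It does not. Extra events in the count can only bring crossing forward, so a 20% cardiac rate still crosses with probability of at least 0.948. Crossing leads to suspension and a review of all safety data, which is not termination.

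Nor does the text reading leave related grade 4 or higher events unwatched. Investigator-judged monitoring is a legitimate choice, and it is backed by serious adverse event reporting (Section 17.2), 24-hour reporting of grade 4 or higher cytopenias and infections (Section 17.2.1) and an institutional monitoring committee for phase I and II trials (Section 16.2). Routing crossings to that committee would be a preference, not the correction of an error.

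Finally, the table was read from a PDF and its row structure may have been lost, so "or" could mean the same boundary applied separately to each class. That would remove the pooling but not the conflict: the text still gives related grade 4 or higher events no number, and the overall crossing probability would be 0.18 under the assumptions above, not 0.1.

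**Conclusion.** The contradiction is established from Section 14.0 alone: text and table disagree on which events count toward a rule that suspends a cohort. The printed operating characteristics are correct for their stated rates, but the 0.1 applies only if the counted event's true rate is about 5.1% or less. Nothing in the documents supports that rate for a composite that includes all related grade 4 or higher events.

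The size of the problem is conditional. At assumed composite rates of 8%, 10%, 15% and 20%, the crossing probability is 0.30, 0.47, 0.80 and 0.95. These figures assume independent patients, a common rate and 41 patients in the cohort. The true rate cannot be read from the documents, so false suspension is a risk that rises steeply with that rate but is not shown to be near-certain. What pooling costs is specificity.

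**What to change.** Reconcile the text and table of Section 14.0 to one event list. State whether ischemic heart disease counts, and whether related grade 4 or higher adverse events, including haematologic ones, count toward the numeric boundary. Which events count is for the sponsor to decide.

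- If only cardiac events count, remove the other class from the table; the current boundary and probabilities can stay for that event.
- If both classes count, either give each its own row or keep one pooled row. In either case, justify the acceptable and unacceptable rates for the event in that row, then recompute and restate the crossing probabilities. With two rows, also give the probability that at least one boundary is crossed.

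The cost is one rewritten paragraph, one revised table and a short exact binomial calculation. Sample size and the primary analysis are untouched.

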- Cycles 7-8: Daratumumab 16 mg/kg day 1; Acetaminophen 650 mg; intravenous Diphenhydramine 25 mg.
- Cycles 2-8: Carfilzomib 56 mg/m² per dose, days 1, 8, and 15
- Cycles 2-8: Lenalidomide 25 mg/day, days 1-21 every 28 days
- Cycles 2: Dexamethasone 40 mg/dose, days 1, 8, and 15; 20 mg/dose day 22
- Cycles 3-4: Dexamethasone 40mg/dose, Days 1, 8 15
- Cycles 5-8: Dexamethasone 20mg/dose, Days 1, 8, 15
- After receiving 4 or more cycles, patients who are considered to be eligible for subsequent high dose therapy/autologous stem cell transplant (ASCT) will be recommended to undergo autologous stem cell harvesting for potential use in the future. For patients who choose to undergo stem cell harvest, the subsequent cycle may be delayed for up to 7 weeks.

Clinical and Correlative Studies - To create a bone marrow (clinical pathology, whole BM lysate, CD 138+ fractions and CD 138- fractions cell sorting with subsequent correlatives on both fractions), peripheral blood, and urine sample bank. These samples may be used to later to evaluate biological activity of daratumumab, carfilzomib, lenalidomide, and dexamethasone. Timepoints and potential analyses are listed below:

Bone Marrow

Sampling Time Points of Bone Marrow correlative studies

- a) Baseline
- b) CR/sCR during cycles 2-and up to 8
- c) End of therapy
- d) 1, 2 and 3 year timepoints after completing therapy (optional)

	Baseline	During Cycles 2-8 if reaches CR/sCR	End of study therapy	1,2, and 3 year timepoints after completing therapy
Pathology/IHC	x	x	x	x
Multiparametric Flow Cytometry	x	x	x	x
FISH/Cytogenetics	x			
Molecular Pathology for light or heavy chain immunoglobulin rearrangement	x	x	x	x
Storage (sorted and whole cell lysate)	x	x	x	x

*Patients undergoing MRD evaluation or End of study evaluation, the first pulled sample will be sent for Multiparametric flow cytometry

- Potential studies on the stored bone marrow samples may include but are not limited to the following:

Bone Marrow Aspirate/Biopsy

Pathology/Immunohistochemistry

Immunohistochemical staining will be assessed using immunohistochemistry markers such as CD 138, light chains, CD56 etc. Microenvironment interactions will also be assessed using various immunohistochemistry markers for osteoblasts, osteoclasts, stromal cells and proteasome components.

Minimal Residual Disease

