Flow cytometry: Immunophenotyping of aberrant plasma cells by flow cytometry currently involves, but is not limited to, the use of the following reagents: CD138, CD19, CD45, CD38, and CD56.

Characteristic changes in immunophenotypically abnormal plasma cells (CD38 bright and/or CD138 positive) include but are not limited to decreased or absent CD19 and CD45, decreased CD38, increased CD56, decreased CD27, decreased CD81, increased CD117. For patients with non-evaluable samples at MRD assessment, patients can opt for repeat MRD assessment or continue to receive a total of 8 cycles of CRd. The first pulled bone marrow sample will be sent for multi-parametric flow cytometry as a priority. Samples will undergo MRD testing per MSK institutional practice, see section 12.0 for further methodology practice.

Molecular pathology: For MRD samples utilizing the NGS LymphoSIGHT™ (Adaptive, CA) platform, the InVivoScript NGS platform, immunoglobulin heavy and kappa chain variable, diversity, and joining gene segments from genomic DNA obtained from CD138+ bone marrow (BM) cell lysate or cell-free supernatant BM aspirate were amplified using universal primer sets as described elsewhere²¹. An MM clonotype was defined as an immunoglobulin rearrangement identified by NGS.

Mass spectrometry based proteomics for minimal residual disease assessment: Serial urine and serum samples will be analyzed to detect clonotypic peptides representing patient's monoclonal immunoglobulin heavy and light chains using high resolution mass-spectrometry-based proteomics.

FISH and cytogenetics

Interphase FISH/cytogenetics will be performed on patients enrolled in this protocol.

DNA-based target mutations

Bone marrow aspirate samples will be analyzed for somatic mutations by exome-sequencing of targeted genes using MSK *myTYPE* platform (or equivalent e.g. MSK Impact Heme). After therapy, perform if response is \leq PR or evidence of gross residual disease on SPEP/UPEP

Cell Sorting and Bone marrow cell lysate

Bone marrow aspirate storage samples will be sorted into CD 138 + and CD 138 – fractions and whole bone marrow cell lysate per HOTB SOP.

Research Blood/Serum and Urine

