5. To create a bone marrow, urine, stool, and peripheral blood sample bank. These samples may be used to later evaluate biological activity of daratumumab, carfilzomib, lenalidomide, and dexamethasone. Potential analyses include sequencing and gene expression profiling on pre and post therapy bone marrow samples, identification of potential biomarkers (blood, urine, stool, bone marrow aspirates) associated with clinical outcomes.

Exploratory Studies:

1. The gene panel myTYPE (or alternative equivalent platform) will explore whether any mutations appear to be associated with response to therapy or toxicity associated with therapy. This analysis is for hypothesis-generation, and all results will be cautiously interpreted. Fisher's exact test may be used to assess any potential association. The variant allele frequency (VAF) will be summarized for each mutation.
2. myTYPE (or alternative equivalent platform) will also be evaluated using samples at the time of progression of disease or during an ongoing response and will be compared to the pre-treatment baseline samples to explore whether pathways leading to emergence of resistance to the drug regimen can be identified. Similar to the previous objective, this aim is for hypothesis generation, and all results will be cautiously interpreted. Changes in the VAF from baseline will be summarized for patients with an ongoing response and for patients who have progression of disease. A paired t-test may be used to further describe this association.
3. To evaluate the effects on stem cell mobilization quality in patients receiving daratumumab, carfilzomib, lenalidomide, and dexamethasone. Examples of data being collected but not limited to will include the following: number of patients undergoing stem cell mobilization, demographics, cycles received prior to stem cell mobilization, CD34 blood

counts prior to collection, total stem cell yield, mobilization failure rates, and subsequent attempts of mobilization.

The proposed study will enroll 41 newly diagnosed multiple myeloma patients seen at MSKCC into each of the two cohorts. Currently, we see over 250 new patients per year and we anticipate enrolling 2-4 patients per month on this study. Thus, we expect to have the study fully enrolled 12-24 months after opening of the study.

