APPENDIX B

To characterize bone marrow aspirate specimens for somatic base mutations and copy number alterations in key cancer-associated genes, we will perform a custom, targeted deep-sequencing assay on matched tumor and normal pairs. The assay, termed *myTYPE* involves massively parallel sequencing, coupled with solution-phase exon capture. The assay will generate high-depth (~1500x) sequencing data for genes causally implicated in myeloma pathogenesis by comprehensive whole exome and whole genome studies. Genes have been selected on the basis of known mutation frequencies in myeloma neoplasms and prior evidence from genomic profiling studies including copy number analysis. *myTYPE* contains genome wide copy number probes, which supports detection of arm level copy number alterations as well as hyperdiploid genomes and the detection of IGH rearrangements. Thus, using *myTYPE* we will establish in-house algorithms to deliver full genome annotation and definition of clonal and subclonal mutation clusters. For studies focusing on characterization of MRD+ cells, samples will be sorted of FACS-Aria Fusion and RNA and DNA will be extracted for bulk sequencing. Clonal architecture of residual disease will be evaluated by single cell transcriptome analysis. The targeted DNA sequencing panel *myTYPE* covers the following:

- Copy number analysis: by including genome wide SNPs at least every 3Mbs
- IgH translocations: by including the hotspot intron In IgH where the vast majority of breakpoints occur
- Amplifications and deletions: we are adding additional SNPs for common amplification and deletions in myeloma, both for chromosomal regions and specific genes i.e. 1q gain and 17p deletion, *MYC* amplification, *CKS1B* amplification, *TP53* deletion, and more.
- Genes (exons) with previously reported recurrent mutations, i.e. *KRAS*, *NRAS*, *BRAF*, *FAM46C*, *IRF4*, *TRAF3*, *TP53*, *CYLD*, *DIS3*, and many more (in total ~110 genes). In addition, we are adding previously mutated and candidate genes in treatment target pathways, i.e. the cereblon pathway, NFkB and BCR pathways, genes within proteasome subunits, as well as targets for novel immunotherapy.

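### The resistance aim summarises VAF change without naming the cell fraction or correcting for tumour content, and its ongoing-response group does not match the Section 10 sequencing rule

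*Combined protocol and SAP*

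**What the plan says.** Section 14.0, Exploratory Studies item 2, uses the myTYPE panel on "samples at the time of progression of disease or during an ongoing response and will be compared to the pre-treatment baseline samples". The purpose is to see whether routes to resistance can be found. The summary is: "Changes in the VAF from baseline will be summarized for patients with an ongoing response and for patients who have progression of disease". It adds: "A paired t-test may be used to further describe this association". It also gives the status of the work: "this aim is for hypothesis generation, and all results will be cautiously interpreted".

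Section 10.0, under DNA-based target mutations, describes the specimen: "Bone marrow aspirate samples will be analyzed for somatic mutations by exome-sequencing of targeted genes". After therapy, sequencing is done if response is at most "PR or evidence of gross residual disease on SPEP/UPEP".

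Other parts of the plan bear on the point:

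- The Section 10.0 marrow table has a row "Storage (sorted and whole cell lysate", ticked at baseline, at CR/sCR, at end of therapy and in yearly follow-up. The text sorts stored aspirate into CD138+ and CD138- fractions. The schedule footnotes link this material to DNA sequencing, but with the words at baseline, even in the post-therapy footnote.
- Appendix B plans matched tumour-normal pairs, about 1500x depth, clonal and subclonal clustering by algorithms still to be established, and cell sorting for studies of MRD+ cells. It says the panel contains "genome wide copy number probes, which supports detection of arm level copy number alterations".
- Marrow at progression is optional though recommended, and progression is not among the listed marrow correlative time points.

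**The concern.** The aim asks which clones expand under treatment. VAF in a marrow sample depends on two things: how many of the cells are tumour, and what share of the tumour carries the mutation. Only the second concerns selection. Treatment is expected to change the first, so an uncorrected change in VAF can report tumour load as if it were resistance biology. It can also hide a subclone that has taken over.

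The second difficulty is who enters the ongoing-response group. Section 14.0 speaks of patients in ongoing response without limit. The Section 10.0 rule reaches patients in PR and those with gross M-protein. CR/sCR, and VGPR detectable only by immunofixation, fall outside it while those states last. The group that is summarised would then be shallower responders, and the analysis text does not say so.

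**Working it through.** The plan gives no sample size, power or numerical target for this aim, so there is no figure to reproduce. The check is how VAF behaves under the stated measure.

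**Inputs.** Depth of about 1500x is from Appendix B. Assay sensitivity of one cell in 100,000 is from Section 12.0. The plasma-cell fractions, CCFs and sorted purities below are assumptions. The documents do contain thresholds of 60% (a qualifying event in Section 6.1) and 5% (the CR ceiling in Section 12.0), but these are not the distribution in this trial.

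**Formula.** With purity p, CCF c, m mutant copies per mutated cell and tumour copy number C, VAF = p·c·m / (p·C + 2(1 − p)). For a heterozygous mutation in a diploid region (m = 1, C = 2) this is VAF = p·c / 2.

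**Examples:**

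| Scenario | Purity | CCF | VAF |
|---|---|---|---|
| No selection, response | 60% → 5% | 1 → 1 | 0.300 → 0.025 |
| No selection, response | 10% → 5% | 1 → 1 | 0.050 → 0.025 |
| No selection, higher load at progression | 30% → 60% | 1 → 1 | 0.150 → 0.300 |
| No selection, lower load at progression | 60% → 10% | 1 → 1 | 0.300 → 0.050 |
| True selection, lower load | 60% → 10% | 0.2 → 1 | 0.060 → 0.050 |
| Sorted, equal purity, no selection | 90% → 90% | 1 → 1 | 0.45 → 0.45 |
| Sorted, equal purity, selection | 90% → 90% | 0.1 → 1 | 0.045 → 0.45 |
| Sorted, unequal purity, no selection | 90% → 50% | 1 → 1 | 0.45 → 0.25 |

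The first row is a 12-fold fall (0.300 / 0.025) with no clonal change. In the fifth row a subclone goes from one fifth of the tumour to all of it, yet VAF falls. Inverting the formula, c = 2·VAF / p, recovers the truth: 2 × 0.060 / 0.60 = 0.2 and 2 × 0.050 / 0.10 = 1.0. The last row shows that sorting alone is not enough if purity differs between the two samples.

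**Paired t-test.** This was simulated for a clonal mutation with no selection: two-sided 0.05, 1500 reads, 4,000 runs, and beta-distributed purity with parameters summing to 10. Rejection rates were:

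| Mean purity | n = 5 | n = 10 | n = 20 |
|---|---|---|---|
| 40% → 40% | 5.5% | 4.7% | 5.2% |
| 90% → 90% | 3.5% | 4.4% | 5.4% |
| 40% → 20% | 42% | 83% | 99% |
| 90% → 70% | 54% | 91% | over 99% |

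The test keeps its level only when mean purity is the same at both times.

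**Limit in deep response.** At one tumour cell in 100,000, expected mutant reads are 1500 × 0.00001 / 2 = 0.0075. MRD-negative marrow carries no usable VAF in bulk sequencing, whatever the sampling rule.

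**The two sections side by side.** PR counts as a response in Section 14.0, so the ongoing-response group is not empty under the Section 10.0 rule. It holds patients in PR, plus those in VGPR whose residual M-protein counts as gross disease, a term left undefined. Progressing patients would normally meet the rule, but only if a marrow is taken.

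**The case against.** The best case for the plan is that most of what is needed is already there: sorted fractions, matched normals, copy-number probes, clonal clustering and sorting of MRD+ cells. On that view Section 14.0 lacks a cross-reference, not a method, and the choice of CCF over VAF can be settled at analysis. The aim is labelled hypothesis-generating, and no endpoint, stopping rule or sample size depends on it. Much of this stands, and it is why the severity is lowest. It does not remove the gap. The only stated measure is VAF change, nothing ties it to the sorted fraction or to a purity estimate, and cautious reading does not repair a measure that can move in the wrong direction.

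Several stronger readings are tempting, and the documents do not support them:

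- *That unsorted marrow will be sequenced.* The fraction is simply not stated.
- *That the aim cannot identify resistance.* A mutation, copy-number change or rearrangement absent at baseline and present at progression can be seen without correcting VAF.
- *That complete responders are never sequenced.* The rule depends on disease state. A complete responder who relapses with measurable M-protein would meet it, and Appendix B provides for sorted MRD+ cells.
- *That the expected CR rate measures the loss.* In the earlier KRd study described in Section 3.0, all 25 CR/sCR patients assessed by flow were MRD-negative. Such samples would be uninformative under any rule.
- *That VAF must rise at progression.* The comparison is with baseline, not nadir, so it may move either way.

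**Conclusion.** The point holds as a cheap improvement of lowest severity. As specified, change in VAF cannot be read as clonal selection unless purity is equal at both time points or is modelled. Under the assumed purities the distortion ranges from a halving to a 12-fold fall with no selection, and it can reverse the sign when selection is real. These sizes are illustrative: they assume heterozygous diploid mutations, and the documents give no purity data for this trial.

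The mismatch between Sections 10.0 and 14.0 does not rest on those assumptions. Read together, they make the ongoing-response group responders with visible residual disease, and the analysis should say so. The aim is weakened rather than defeated, and the primary endpoint is untouched.

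**What to change.** 1. In Section 14.0, make the measure the change from baseline in purity- and copy-number-corrected CCF. Use the stored CD138+ fraction at both time points where DNA yield allows, and estimate purity from the panel's own copy-number and SNP content. Report raw VAF descriptively beside it, with the purity of each sample. Apply any paired test to CCF.
2. Reconcile Sections 10.0 and 14.0. Define the ongoing-response group as responders with recoverable residual clonal cells, including sorted MRD+ cells under Appendix B. State that MRD-negative samples contribute no post-therapy value.
3. Correct the post-therapy schedule footnote so that stored fractions are linked to sequencing at the later time points as well as at baseline.
4. List progression as a marrow correlative time point for when a marrow is being taken anyway.

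The cost is wording in two sections and some added bioinformatics, with the same panel and material already stored. The downside is fewer evaluable pairs and some samples with too little CD138+ DNA.
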